## Introduction

Invasive intracranial pressure monitoring takes on essential importance in patients with traumatic brain injury and in all cerebral pathologies in which intracranial hypertension is the main cause of death.

The dose of intracranial pressure (ICP), meant as the time for which intracranial pressure exceed the reference values, has been related to poor outcome. “Time is brain” is a concept which highlights the importance of preempt and perform the proper therapeutic strategies, in order to reduce complications in the context of a rapidly and irreversibly compromised cerebral tissue as a result of a brain injury.

On these bases, it is essential to perform an accurate intracranial pressure monitoring as soon as possible, to detect and possibly treat intracranial hypertension, which would definitively compromise brain parenchyma.

Invasive intracranial pressure monitoring performed by placing an intracerebral catheter (intraventricular or intraparenchymal) is currently the gold standard technique for continuous ICP invasive monitoring.

This maneuver has usually been performed by neurosurgeons, but in an effort to optimize as much as possible the timing of ICP monitoring, reducing time between urgent request for invasive ICP monitoring placement and the placement itself, this procedure (specifically intraparenchymal catheter placement) has more often been carried out by intensive care physicians at the bedside, in the last few years.

In the setting of clinical practice, multidisciplinary management of intracranial pressure handling and treatment is therefore achieved by joint decisions between neurosurgeons and intensive care physicians, but differences in logistic matters and in the executive availability could impact on the dose of intracranial pressure to which patient is exposed.

The aim of this study is to compare timing of invasive intracranial pressure monitoring placement performed by intensive care physicians and neurosurgeons and to detect possible differences in the incidence of complications between the two groups.

## **Aim of the study**

### Primary outcome:

- To compare timing of invasive intracranial pressure monitoring performed by intensive care physicians and neurosurgeons, from time T1 (defined as the moment in which invasive intracranial pressure monitoring indication is stated) to time T2 (skin incision).

### Secondary outcome:

- Comparative evaluation of post-procedural complications (meningitis, catheter-placement related bleedings, wrong placement) between intensivists and neurosurgeons
- Length of ICU stay, length of hospital stay, duration of mechanical ventilation, Glasgow Outcome Score at 3 months.
- To compare timing and complications of invasive intracranial pressure monitoring between placement of intraparenchymal catheters and extraventricular drains

## Materials and methods

Inclusion criteria:

- All patients with acute cerebral pathology with urgent indication to invasive intracranial pressure monitoring (intraparenchymal and intraventricular)
- Age greater than or equal to 18 years

Exclusion criteria:

- Patients in whom indication to intraventricular catheter placement is stated for reasons other than the need of ICP monitoring (e.g. CSF drainage)
- Patients in whom indication to invasive intracranial pressure monitoring is not an urgent request
- Patients in whom a significant coagulation disorder is a contraindication for procedure

Timings are defined as:

[figure not shown]
- T0: suspect of pathology at risk for developing intracranial hypertension
- T1: neurointensive and neurosurgical indication to invasive ICP monitoring (it could be the time when brain CT is performed or, in the absence of a brain CT, the time at which indication to invasive ICP monitoring is stated)
- T2: skin incision at skull for BOLT/EVD placement

Place of positioning:

The place (intensive care unit or operating room, specifying if it's a dedicated OR or a surgical unit) where the procedure is carried out must be declared.

Complications which will be analyzed:

- Catheter-related intracranial bleedings, with or without the need of neurosurgical operation (all the patients enrolled in the study must have been screened for coagulation disorders)
- Meningitis (actually related to procedure), with microorganism causing meningitis demonstrated by culture (not a contaminant microorganism)
- Wrong positioning of catheter and/or its malfunction (e.g., a correct placed catheter penetrates the parenchyma for few millimeters/absence of ICP wave). Malfunction is considered as such if it occurs up to 12 hours after placement.

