## Statistical analysis plan

Delta time in the placement of invasive ICP monitoring is assumed as  $T2-T1$ , declared in minutes.

Typology operator (neurosurgeon vs intensivist) impact on delta time will be evaluated through a multilevel model elaborated with a linear mixed model. The model will assume the center in which the maneuver is carried out as clustering factor. The place where the maneuver is carried out (intensive care unit vs operating room) and the confidence in performing the procedure (routine vs sporadic, defined as less than 5 times a year) will be assumed as covariates.

The incidence of complications, valued as a binary variable, will be evaluated through logistic model GLMM (generalized linear mixed model) with the organization exposed in the dedicated data element.

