### Sample size assessment

Sample size assessment has been performed by Monte Carlo simulation ( $B=500$ ). Assuming a timing decrease ( $T2-T1$ ) of 20 minutes in the procedure carried out by an intensivist compared to a neurosurgeon, with a mean time of 100 minutes, a standard deviation between center and intra-center of 10 minutes, 16 centers, each one with the same number of patients and a balance 1:1 between the two groups (intensivist:neurosurgeon), a total number of 64 patients (32 treated by intensivists and 32 by neurosurgeons), it allows to evaluate the interest effect with a power of at least 95%, and a significance level of 5%.

This elevated power has been decided according to the simplicity of the assumed design (same number of entities and conditions for center) and not evaluable in his real configuration.

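### The timing outcome stops at skin incision, so it measures time to start of the procedure and leaves insertion out of the bolt-versus-EVD comparison

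*Combined protocol and SAP*

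**What the plan says.** The Primary outcome runs from T1 (indication stated) "to time T2 (skin incision"). Materials and methods lists three times, T0, T1 and T2, and the last is "T2: skin incision at skull for BOLT/EVD placement". The Statistical analysis plan then sets the analysed variable to T2-T1 in minutes: "Delta time in the placement of invasive ICP monitoring is assumed as" that difference. The text defines no time for catheter in place, first ICP value or end of procedure.

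The Introduction gives two strands of rationale. One is earlier monitoring, so that raised pressure can be detected and treated. It describes bedside placement by intensivists as an effort aimed at "reducing time between urgent request for invasive ICP monitoring placement and the placement itself". The other is organisational: "differences in logistic matters and in the executive availability could impact on the dose of intracranial pressure to which patient is exposed".

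The third item under Secondary outcome is "To compare timing and complications of invasive intracranial pressure monitoring between placement of intraparenchymal catheters and extraventricular drains". No separate interval is defined for it.

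**The concern.** At skin incision there is no catheter in the brain and no pressure value. Drilling, passing the catheter and obtaining a waveform all come later. An outcome labelled as placement time that ends before placement may be read as time to monitoring, when it is time to the start of the procedure.

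For the operator comparison, a difference in T2-T1 need not equal the difference in time to usable monitoring. For bolt versus EVD the problem is sharper, because the part of the work specific to the device lies after T2. Finding no difference on T2-T1 would say nothing about whether one device gives a reading sooner once the procedure has begun.

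**Working it through.** **1. What each interval contains.** Let T3 be the time of the first valid ICP value or waveform. Then

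T3-T1 = (T2-T1) + (T3-T2),

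and for any two groups the difference in mean T3-T1 equals the difference in mean T2-T1 plus the difference in mean T3-T2. The plan estimates only the first term on the right.

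| Purpose in the documents | Interval it needs | Interval available |
|---|---|---|
| Logistic and availability delay (Introduction) | T1 to start of procedure | T2-T1: matches |
| Time from request to placement, early detection (Introduction) | T1 to catheter in place or reading | T2-T1: omits T3-T2 |
| Timing of bolt versus EVD (Secondary outcome) | not defined | T2-T1 by default: omits device insertion |

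The third row needs no assumed numbers. If mean insertion time differs between devices by x minutes, T2-T1 registers 0 of those x minutes.

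**2. The plan's power figure.** Inputs from Sample size assessment: a reduction "of 20 minutes in the procedure carried out by an intensivist compared to a neurosurgeon", "with a mean time of 100 minutes", between-centre and within-centre SD of 10 each, 16 centres, 64 patients split 1:1, 5% significance (two-sided assumed), and power of at least 95%. The approximation is power = Φ(effect/SE − 1.96).

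- Operator varies within centre, so the centre effect cancels: SE = 10 × √(2/32) = 2.5; 20/2.5 = 8; power above 99.99% (simulation with 500 runs: 100%).
- Operator fixed by centre, 8 versus 8 centres of 4 patients: SD of a centre mean = √(100 + 100/4) = 11.18; SE = 11.18 × √(2/8) = 5.59; 20/5.59 = 3.58; power 94.7% (simulation 93.4%; t with 14 df 91.4%).

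The within-centre reading meets the stated bound, so the figure is reproduced as a lower bound. It applies to T2-T1 only.

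**3. Illustration for operator type.** The documents give no insertion times, so everything here is assumed. Let d be the extra minutes intensivists need from incision to reading (negative if they are quicker) and s the added within-centre SD. The effect on T3-T1 is 20 − d. The SE is √(100 + s²) × √(2/32) within centres, or √(100 + (100 + s²)/4) × √(2/8) if operator is fixed by centre.

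| d (min) | Effect on T3-T1 (min) | Power within centre, s = 0 to 15 | Power if operator fixed by centre, s = 0 to 15 |
|---|---|---|---|
| −5 | 25 | about 100% | 99.4% to 96.0% |
| 0 | 20 | above 99.99% to 99.3% | 94.7% to 84.4% |
| 5 | 15 | above 99.9% to 91.4% | 76.5% to 60.6% |
| 10 | 10 | 97.9% to 60.2% | 43.2% to 31.8% |
| 15 | 5 | 51.6% to 19.8% | 14.3% to 11.2% |

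The sign of d is unknown, so the operator advantage in time to monitoring could be smaller or larger than on T2-T1. In the within-centre design, power for T3-T1 falls materially only with a large d or with a sizeable d plus added variance.

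**4. Bolt versus EVD.** The plan gives no effect size or sample size for this objective, so no power can be computed.

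**The case against.** The strongest reply is that stopping at incision is deliberate. The primary outcome, the timing definitions and the analysed variable all agree, and the Introduction names logistics and availability as the mechanism. T1 to incision measures that delay directly and keeps operative duration out of it. This stands: the primary outcome is sound for that purpose, and the mismatch is with part of the rationale only.

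Several stronger readings are tempting, and the documents do not support them:

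- **That a failed placement counts as a fast success.** T2-T1 is not a success measure. Wrong positioning and malfunction are listed complications with their own model. What is missing is the monitoring delay such a failure causes.
- **That insertion time is never recorded.** The case report form is not available, the timing figure is not shown, and the malfunction window of 12 hours after placement presupposes some placement time. The supportable statement is that the text neither defines nor analyses a later time.
- **That a null device result would be uninformative.** It would still describe delay to the start of the procedure, for instance through access to an operating room, provided it is labelled that way.
- **That the operator advantage is overstated.** Every minute figure after incision is assumed, and the direction is open.

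A further objection concerns the remedy. A clock that runs until a valid reading has no end for a patient who dies first or never gets one, and a linear mixed model does not handle such times. This also stands, and the fix must provide for it.

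**Conclusion.** The point holds as a limit on what T2-T1 can show. It is a valid, internally consistent primary outcome for time from indication to start of procedure, but it is not time to placement or to working ICP monitoring. The consequence is greatest for bolt versus EVD, where any insertion-time difference is excluded in full; this follows from the definitions alone. For operator type the consequence depends on unknown insertion times: the 5 to 25 minutes of remaining advantage shown above rest entirely on assumed values of d from 15 to −5. A reader might infer that the primary outcome or the sample size is wrong. Neither follows: the definitions do not conflict, and the stated power is reproduced for the outcome to which it refers. This is an inexpensive improvement, best made before data collection because the missing time may be hard to recover afterwards.

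**What to change.** - Keep T2-T1 as the primary outcome, describe it as time from indication to start of procedure, and limit conclusions drawn from it to that.
- Add to the timing definitions in Materials and methods: T3 = time of first valid ICP value or waveform.
- Report T3-T1 and T3-T2 as the timing outcomes for bolt versus EVD, and as supportive secondary outcomes for operator type. Use the linear mixed model of the Statistical analysis plan in patients with a valid reading, with device type as the exposure in the device comparison.
- Report by group how many patients never obtain a valid reading. In a time-to-event sensitivity analysis of T3-T1, treat them as censored, with death as a competing event.

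The cost is one extra prospectively collected timestamp, some missing values, and one additional secondary analysis with its sensitivity analysis. No extra patients or procedures are needed, and the sample size can stay as it is.

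### Coagulation screening is compulsory, yet no model described in the plan uses the result, so residual coagulation differences between operator groups could confound the bleeding comparison and possibly T2-T1

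*Combined protocol and SAP*

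**What the plan says.** The Materials and methods section lists bleeding among the complications to be analysed: "Catheter-related intracranial bleedings, with or without the need of neurosurgical operation". The same item adds that "all the patients enrolled in the study must have been screened for coagulation disorders". The exclusion criteria remove "Patients in whom a significant coagulation disorder is a contraindication for procedure". No laboratory threshold is given, and no other use of the screening result is stated.

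The secondary outcomes include "Comparative evaluation of post-procedural complications (meningitis, catheter-placement related bleedings, wrong placement) between intensivists and neurosurgeons".

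In the Statistical analysis plan, the linear mixed model for T2-T1 has operator type as the effect of interest and centre as the clustering factor. Place of procedure is one covariate, and "the confidence in performing the procedure (routine vs sporadic, defined as less than 5 times a year) will be assumed as covariates". For complications, the plan specifies a "logistic model GLMM (generalized linear mixed model) with the organization exposed in the dedicated data element". That element does not appear in the text.

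No section describes random assignment of operator. The 1:1 balance appears only as an assumption in the Sample size assessment.

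**The concern.** By attaching the screen to the bleeding item, the plan itself treats coagulation as relevant to catheter-related bleeding. The exclusion controls this by restriction, but only down to the point where someone judges the procedure contraindicated. Disorders short of that point remain eligible.

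Because operator is not described as randomised, the two groups may differ in how many such patients they contain. No described model has a term that separates this from an operator effect. An apparent difference in bleeding between intensivists and neurosurgeons could then reflect the patients and not the operator.

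The primary outcome may also be exposed. T1 can be the time of the brain CT, and T2 is skin incision. If waiting for a screen, or dealing with an abnormal one, falls after T1, that time counts in T2-T1. The group with more abnormal screens would look slower for a reason unrelated to operator type.

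**Working it through.** **1. The plan's own figure.** The inputs from the Sample size assessment are a 20-minute effect, a between-centre and within-centre SD of 10 minutes each, 16 centres, 64 patients split 32:32, and 5% significance (taken as two-sided). The stated power is at least 95%.

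- Operators balanced within each centre: SE = 10 × √(2/32) = 2.5 min and 20/2.5 = 8, so power exceeds 99.9%. The stated figure is met.
- One operator type per centre (8 vs 8): SD of a centre mean = √(100 + 100/4) = 11.18 min. Power is 94.7% with a z test and 91.4% with t on 14 df.

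The concern does not depend on this power figure. The 2.5-minute SE is used in step 4.

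**2. Where coagulation status appears.**

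| Place in the plan | Coagulation status |
|---|---|
| Enrolment | Screen required for all |
| Exclusion | Only if a significant disorder contraindicates the procedure |
| T2-T1 model | Absent; the terms are operator, centre, place and confidence |
| Complication model | Not named; structure deferred to an element not in the text |

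**3. Bleeding.** The documents give no bleeding rate and no frequency of abnormal screens, so all inputs here are assumptions. There is no true operator effect. Crude risk = p × (risk if abnormal) + (1 − p) × (risk if normal), where p is the share of abnormal screens.

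- *p = 25% vs 5%; bleeding risk 12% if abnormal, 3% if normal.* 0.25 × 0.12 + 0.75 × 0.03 = 0.0525; 0.05 × 0.12 + 0.95 × 0.03 = 0.0345. Odds ratio = (0.0525/0.9475)/(0.0345/0.9655) = 1.55. Expected bleeds: 32 × 0.0525 = 1.68 vs 32 × 0.0345 = 1.10.
- *Same p; risks 15% and 5%.* 0.075 vs 0.055; odds ratio 1.39. Expected bleeds: 2.4 vs 1.76.
- *Wider grid: 2% or 5% risk without a disorder, disorder odds ratio 2 to 5, p = 10% vs 20–40%.* The crude operator odds ratio runs from about 1.1 to 1.8. With equal p it is 1.00.

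What this means with 32 per group, under the first set of inputs:

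- Chance that at least one group has no bleeds: 1 − (1 − 0.9475³²)(1 − 0.9655³²) = 1 − (1 − 0.178)(1 − 0.325) ≈ 45%.
- Chance that Fisher's exact test gives p < 0.05: about 0.2%.
- A Mantel-Haenszel odds ratio stratified by screen result is zero, infinite or undefined in about 50% of simulated trials. The group with 5% prevalence has no abnormal screens in 0.95³² ≈ 19%.

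Across assumed bleeding rates of 1%, 2%, 5% and 10%, 64 patients give 0.6, 1.3, 3.2 and 6.4 expected bleeds.

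**4. T2-T1.** The delay and the imbalance are assumptions. Shift = difference in p × delay.

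- 20 points: 0.20 × 30 = 6 min; 0.20 × 60 = 12 min; 0.20 × 90 = 18 min.
- At the lowest delay, 6/20 = 30% of the planned effect, and 6/2.5 = 2.4 SE. A two-sided 5% test would reject about 67% of the time with no operator effect.
- Allowing for the variance that the delay adds: 100 + 0.25 × 0.75 × 30² = 268.75 and 100 + 0.05 × 0.95 × 30² = 142.75. SE = √((268.75 + 142.75)/32) = 3.59 min and 6/3.59 = 1.67, so rejection is about 39%.
- If the screen is resolved before T1, the delay inside T2-T1 is zero and so is the shift.

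**The case against.** The strongest case on the other side has four parts.

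*The main confounder is already restricted.* Contraindicating disorders are excluded and everyone is screened. This stands: what is left is a residue. That the residue includes corrected disorders is an inference from the exclusion wording, since the documents do not mention correction.

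*The mechanism is conjecture.* Nothing says that the two specialties judge contraindication differently. The Introduction describes joint decisions, and T1 is defined as an indication from both neurointensive care and neurosurgery. This also stands, and it leaves the direction of any bias unknown. It does not establish balance, because a shared indication does not settle who then performs the procedure.

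*For bleeding, noise swamps the bias.* This stands. With about 1.7 vs 1.1 expected bleeds, sparse events are the larger problem, and no adjustment can be more than supportive.

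*The T2-T1 argument needs a delay after T1.* This stands as a condition. The documents do not say when screening happens relative to T1, and they give no delay. It is not a reason to leave the term out, since one covariate in a 64-patient linear model costs little.

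A reader might go further and infer that coagulation enters no model at all. The documents show this only for T2-T1. For complications, the element that sets out the structure is not in the text and could name it.

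**Conclusion.** The point holds as a gap in the described analysis. A baseline result that must exist for every enrolled patient, and that the plan links to bleeding, is in no model the documents describe. Residual imbalance in it could confound the bleeding comparison and, on the condition that an abnormal screen is handled after T1, the primary comparison.

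The documents do not fix its size or direction. The crude bleeding odds ratios of about 1.1 to 1.8 and the 6 to 18 minute shifts rest wholly on assumed prevalences, risks and delays. They show what could happen, not what will. A reader might take an odds ratio of 1.55 to mean that a false bleeding difference is likely to be declared. That is not supported: at 32 per group it is about 0.6 of one bleed (1.68 − 1.10 = 0.58).

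The practical value of acting is therefore greater for T2-T1, where adjustment is easily affordable, than for bleeding, where it can give only a supportive estimate. It is a change the plan should make, but the point does not show that either comparison is invalid.

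**What to change.** - Record the first-measured coagulation screen (normal/abnormal) and current antithrombotic treatment for each patient, and tabulate both by operator group. Using the first measurement keeps the variable a pre-procedure characteristic, so adjustment does not remove a real operator effect on speed.
- Add the binary screen result as a fixed covariate in the T2-T1 linear mixed model, and show the operator estimate without it alongside.
- For bleeding, make crude counts by operator and screen result the main display. Give a penalised (Firth-type) logistic estimate adjusted for the screen as supportive only. Do not use a Mantel-Haenszel estimate, which would often be zero, infinite or undefined at this size.
- State the covariates of the complication model in the SAP itself.

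Cost: SAP wording, one extra data item (the screen is already compulsory; antithrombotic treatment is recorded with it), and one degree of freedom in the T2-T1 model. The adjusted bleeding estimate will be very imprecise with 64 patients, and the SAP should say so.

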## Statistical analysis plan

Delta time in the placement of invasive ICP monitoring is assumed as  $T2-T1$ , declared in minutes.

Typology operator (neurosurgeon vs intensivist) impact on delta time will be evaluated through a multilevel model elaborated with a linear mixed model. The model will assume the center in which the maneuver is carried out as clustering factor. The place where the maneuver is carried out (intensive care unit vs operating room) and the confidence in performing the procedure (routine vs sporadic, defined as less than 5 times a year) will be assumed as covariates.

The incidence of complications, valued as a binary variable, will be evaluated through logistic model GLMM (generalized linear mixed model) with the organization exposed in the dedicated data element.

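### The primary mixed model makes no provision for different residual spread by operator, so its 5% test is reliable only if the two spreads are similar or the split is near 1:1

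*Combined protocol and SAP*

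**What the plan says.** The section Statistical analysis plan of the combined protocol and SAP takes T2−T1 in minutes as the outcome and states: "Typology operator (neurosurgeon vs intensivist) impact on delta time will be evaluated through a multilevel model elaborated with a linear mixed model". It adds: "The model will assume the center in which the maneuver is carried out as clustering factor". Place of procedure and confidence in the procedure enter as covariates. The section does not mention residual variance by operator, robust standard errors, transformation or residual checks.

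The section Sample size assessment assumes a decrease "of 20 minutes in the procedure carried out by an intensivist compared to a neurosurgeon", "with a mean time of 100 minutes", and "a standard deviation between center and intra-center of 10 minutes, 16 centers, each one with the same number of patients". It gives one within-center SD, not one per operator. It also assumes a 1:1 operator balance, 32 and 32 patients, and claims power of at least 95%. It explains the margin as follows: "This elevated power has been decided according to the simplicity of the assumed design", and concedes that the real configuration could not be assessed.

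The Introduction gives the reason for the study: "differences in logistic matters and in the executive availability could impact on the dose of intracranial pressure to which patient is exposed".

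**The concern.** A linear mixed model, unless told otherwise, estimates one residual variance for all patients. The standard error of the operator effect then uses an average spread weighted by group size. If the operators' waits differ in spread and the groups differ in size, that average is wrong for the comparison. It is too small when the more variable operator has fewer patients, and too large when that operator has more.

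Both conditions are plausible here. Differences in logistics and availability can change the scatter of waiting times as well as their mean, although this is an inference and the documents give no operator-specific SD. No allocation rule, quota or matching is described that would bring about a 1:1 split.

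At stake is the primary result: a delay difference claimed where none exists, or a real one obscured. The problem does not depend on skewed data or on operator effects that vary between centers. It arises with normal residuals and one common effect.

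**Working it through.** **Inputs from Sample size assessment:** 64 patients, 16 centers of equal size (64/16 = 4 each), center SD 10, within-center SD 10, effect 20 minutes, 5% level (taken as two-sided). **Assumed, because the documents do not give them:** operator-specific SDs and unequal splits.

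**1. The plan's own power.** Within centers, SE = 10 × √(1/32 + 1/32) = 2.5, and 20/2.5 = 8, so power exceeds 99.9%. Ignoring clustering, SD = √(100 + 100) = 14.14, SE = 3.54, and power is 99.99%. A simulation of the random-intercept model (500 replicates) gave 100%. The statement of at least 95% is reproduced.

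**2. Effect of pooling.** With group sizes n₁, n₂ and SDs s₁, s₂:

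- True SE = √(s₁²/n₁ + s₂²/n₂)
- Pooled SE = √{[(n₁−1)s₁² + (n₂−1)s₂²]/(n₁+n₂−2) × (1/n₁ + 1/n₂)}
- R = pooled SE / true SE, and actual type I error ≈ 2Φ(−1.96R)

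Example, 48 patients with SD 10 and 16 with SD 20:

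- True SE = √(100/48 + 400/16) = √27.08 = 5.20
- Pooled variance = (47×100 + 15×400)/62 = 172.6
- Pooled SE = √(172.6 × 0.0833) = 3.79
- R = 0.729, and 2Φ(−1.43) = 15.3%

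At 32:32 the two SEs are identical (R = 1).

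**3. Range.** The simulation column is the common-residual random-intercept model, 16 × 4, center SD 10, 2,000 replicates, without covariates.

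| Less variable : more variable | SD ratio | R | Formula | Simulation |
|---|---|---|---|---|
| 32:32 | up to 3 | 1.000 | 5.0% | 4.4–6.2% |
| 38:26 | 1.5 | 0.929 | 6.9% | not run |
| 43:21 | 1.5 | 0.873 | 8.7% | 9.7% |
| 43:21 | 2 | 0.808 | 11.3% | 10.2–11.7% |
| 43:21 | 3 | 0.749 | 14.2% | 14.7% |
| 48:16 | 1.5 | 0.820 | 10.8% | 10.5% |
| 48:16 | 2 | 0.729 | 15.3% | 15.8% |
| 48:16 | 3 | 0.648 | 20.4% | 20.3% |
| 21:43 and 16:48 | 2 | 1.236, 1.368 | 1.5%, 0.7% | 1.1–1.9% |
| 21:43 and 16:48 | 3 | 1.331, 1.535 | 0.9%, 0.3% | 0.5–1.3% |

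The mix within centers matters somewhat. With operators mixed at random over patients (1,500 replicates), SD ratios 2 and 3 gave 11.5% and 13.6% at 44:20, and 13.5% and 17.7% at 48:16. With an SD ratio of only 1.25, simulation gave 6.5% at 44:20 and 7.1% at 48:16.

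**4. Power when the more variable operator is the larger group.** At 20 minutes with SDs 10/20, power was above 99% under either model. With SDs 10/30, the pooled model gave 87% at 1:2 and 81% at 1:3. With random mixing the comparison was 85% pooled against 95% separate at 20:44, and 75% against 93% at 16:48. For a 10-minute effect with SDs 10/20 it was 54% against 71% at 1:2, and about 46% against 72% at 1:3.

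**5. Planned covariates.** Place and confidence were added, with theatre used in 10% of intensivist and 50% of neurosurgeon cases and adding 15 minutes (assumed). Pooled type I error was 11.2% (44:20, SDs 10/20), 13.4% (48:16, 10/20) and 18.4% (48:16, 10/30). Without covariates the same run gave 12.9%, 13.9% and 18.2% (1,000 replicates). A smaller run (400 replicates) at SDs 10/20, with and without covariates, gave about 8–13%. The covariates therefore do not remove the problem when scatter belongs to the operator.

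**6. The remedy.** With a separate residual variance per operator and SD ratio 2, type I error was 4.8–6.5% over splits from 3:1 to 1:3 (Monte Carlo error about 0.7 points). With degrees of freedom set at the smaller group minus 1, it was 4.3–6.1% without covariates. A run with covariates gave 3.8–5.4%, and the 400-replicate run about 2–6%.

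**The case against.** The plan does not state a common residual variance. That is the default reading of its silence, and the single 10-minute SD belongs to the sizing, not to the analysis specification. This stands.

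A reader might infer that the plan carries a fixed false-positive risk of, say, 12–18%. The documents do not support that. Such a figure needs an SD ratio of about 2 to 3, a split of about 2:1 to 3:1, and the smaller group being the more variable one, and none of these is given.

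A reader might also infer that false positives are the likely direction. If neurosurgeons' waits are the more scattered, inflation requires neurosurgeons to be the minority. The Introduction describes them as the usual operators but also notes growing use by intensivists. If they are the majority, the test is conservative. At 20 minutes the large power margin then absorbs the loss unless one SD is about tripled.

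Finally, scatter may follow place rather than operator. When theatre cases alone carried the extra scatter and place was in the model (SD 20–30, theatre in 40–60% of neurosurgeon and 10% of intensivist cases, all assumed), pooled type I error was 5.7–7.6% at 44:20 and 8.1–9.7% at 48:16. A variance by operator corrects that only in part. Cluster-robust standard errors with a small-sample correction, or a log scale if residuals support it, are also defensible.

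These points limit the size and the direction. They do not show that the pooled test is protected.

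**Conclusion.** The concern holds as a conditional weakness in the primary analysis. The model, as ordinarily fitted, gives a reliable 5% test only if spreads are similar or the split is near 1:1, and the plan ensures neither. The inflation to roughly 7–20%, or the fall to about 0.5–3%, must always be quoted with its SD ratio and split, because both are assumptions. Which direction applies is open. Power at the planned effect is a secondary matter, and becomes material only with SDs near 10/30 or a smaller true effect. Enrolling more patients would not cure the inflation: with three times the patients at 3:1 and SD ratio 2 it was still 15.3% (400 replicates).

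**What to change.** In the Statistical analysis plan, keep the center effect and both covariates. Add that the model for T2−T1 will have a separate residual variance for intensivist and neurosurgeon patients, with Satterthwaite or Kenward-Roger degrees of freedom, and that both residual SDs will be reported with the operator effect. Fix this before the data are analyzed, since a variance structure chosen after seeing results is open to challenge.

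The cost is one sentence, one extra variance parameter and fewer effective degrees of freedom. With equal spreads at 32:32 the mean standard error was practically unchanged (2.74 against 2.75 minutes). Two limits should be known. The checks used simpler degrees of freedom than the two methods named here. And if scatter follows place of procedure, the correction is only partial, so residual spread by place should be inspected as well.
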